***Visit 3 (Day 2 after immunization):***

The following procedures are performed at Visit 3:

- Physical examination.
- Body temperature measurement ( $t^\circ$ ).

---

Strictly confidential. Proprietary Information.  
[name]

- Measurements of vital functions (pulse, SBP, DBP).
- Neurological examination.
- Laboratory investigations:
  - Blood hematology (hemoglobin, RBCs, hematocrit, platelets, WBC and WBC differential [neutrophils, lymphocytes, monocytes, eosinophils, basophils], ESR).
  - Blood biochemistry (glucose, urea, creatinine, total bilirubin, total protein, ALT, AST, AP).
  - Urine test with sediment microscopy (specific density, protein, sugar, RBC, WBC).
- Review of volunteer's diary.
- Assessment for exclusion criteria.
- Recording of concomitant therapy.
- Recording local and systemic reactions, adverse events, and intercurrent disorders.

***Visit 4 (Day 3 after immunization) and Visit 5 (Day 4 after immunization):***

The following procedures are performed at Visits 4 and 5:

- Physical examination.
- Body temperature measurement ( $t^\circ$ ).
- Review of volunteer's diary.
- Assessment for exclusion criteria.
- Recording of concomitant therapy.
- Recording local and systemic reactions, adverse events, and intercurrent disorders.

***Visit 6 (Day 5 after immunization):***

The following procedures are performed at Visit 6:

- Physical examination.
- Body temperature measurement ( $t^\circ$ ).
- Measurements of vital functions (pulse, SBP, DBP).
- Review of volunteer's diary.
- Assessment for exclusion criteria. Recording of concomitant therapy.
- Recording local and systemic reactions, adverse events, and intercurrent disorders.

***Visit 7 (Day 22±1 after immunization):***

The following procedures are performed at Visit 7:

- Physical examination.
- Body temperature measurement ( $t^\circ$ ).

Strictly confidential. Proprietary Information.  
[name]

- Measurements of vital functions (pulse, SBP, DBP).
- Laboratory investigations:
  - Blood hematology (hemoglobin, RBCs, hematocrit, platelets, WBC and WBC differential [neutrophils, lymphocytes, monocytes, eosinophils, basophils], ESR).
  - Blood biochemistry (glucose, urea, creatinine, total bilirubin, total protein, ALT, AST, AP).
  - Urine test with sediment microscopy (specific density, protein, sugar, RBC, WBC).
  - Blood collection for IgE test.
  - Blood collection for serology (serum antibody titer).
  - Urine test for pregnancy (only for female subjects).
- Interviewing on ARI symptoms within the period.
- Review and return of the volunteer's diary.
- Assessment for exclusion criteria.
- Recording of concomitant therapy.
- Recording adverse events and intercurrent disorders.

***Telephone calls (Visits 8–11):***

Telephone calls are made on Day 43±5 (Visit 8), Day 64±5 (Visit 9), Day 122±5 (Visit 10), Day 180±5 (Visit 11) and included the following procedures:

- Interviewing on ARI symptoms within the period.
- Assessment for exclusion criteria.
- Recording of concomitant therapy.
- Recording adverse events and intercurrent disorders.

**3.3. Measures for minimization / elimination of subjectivity**

Subjectivity in the study is minimized / eliminated due to randomization and the double-blinded design of the study.

**3.3.1. Randomization**

The immunization group was determined randomly. Randomization will be based on a computer-generated randomization algorithm (randomization list), where each volunteer will be assigned a randomization number. That number will define the immunization group (A, B, or C) according to the randomization plan. That number will be assigned to the study subject for the entire period of the study and will be documented in volunteer's CRF.

The volunteers will be randomized into 3 groups (at a ratio of 1:1:1). A block randomization method is used. An interactive web-response system (IWRS) with technical support service will be used for randomization.

---

Strictly confidential. Proprietary Information.  
[name]

Investigators will be trained on working with IWRS system, and IWRS user guide will be handed out to all of them.

An identification name (ID) and a password will be used to access the system. These identifiers will be given to the authorized staff member of the investigation site prior to study initiation. Upon the volunteer randomization, the investigator receives information through the IWRS system on volunteer assignment to one of the vaccination groups that will be given to the volunteer during the study.

Volunteer stratification will be performed in the IWRS system according to the age and gender.

In an emergency medical case, the investigator can obtain information about a vaccine received by a volunteer through the IWRS system. Information about storage and unblinding of randomization codes is provided in Section 3.8.

### **3.3.2. Blinding**

This study is double-blind, neither the doctor nor the volunteer will know what kind of vaccine the study participant will receive.

### **3.4. The treatment used in the study, dosages, regimens, dosage form, packaging, labeling, and storage of study drugs**

All the vaccines related to this study will be stored away from other vaccines and drugs in a safe place under relevant storage conditions with temperature control. *All vaccines related to this study will be checked for the expiry date before use. Study subjects cannot be immunized using vaccines with expired date.*

#### **Treatment (immunization), dosages, dosing regimen:**

This study includes 3 study groups:

- Group A: Grippol® Quadri, quadrivalent inactivated subunit influenza vaccine, suspension for intramuscular and subcutaneous administration.
- Group B: Grippol® Plus, trivalent inactivated polymer-subunit influenza vaccine, based on type B influenza virus of Yamagata lineage, suspension for intramuscular and subcutaneous injections.
- Group C: Grippol® Plus, trivalent inactivated polymer-subunit influenza vaccine, based on type B influenza virus of Victoria lineage, suspension for intramuscular and subcutaneous injections.

**Dosing:** All the vaccines used in the study are administered as a single intramuscular injection of 0.5 ml (1 dose) into the upper third of the outer surface of the shoulder (the deltoid muscle).

Strictly confidential. Proprietary Information.  
[name]

### **Description of study vaccines:**

Grippol® Quadri, a quadrivalent inactivated subunit influenza vaccine:	
INN or generic name:	Influenza vaccine [inactivated] + Azoximer bromide
Dosage form:	suspension for intramuscular and subcutaneous injection.
Composition:	
One immunizing dose (0.5 ml) contains:
 
Active ingredients:
 

• Influenza type A virus (H1N1) antigen with hemagglutinin - 5 µg.

• Influenza type A virus (H3N2) antigen with hemagglutinin - 5 µg.

• Influenza type B virus (Yamagata lineage) antigen with hemagglutinin, 5 µg.

• Influenza type B virus (Victoria lineage) antigen with hemagglutinin, 5 µg.

• Polyoxidonium®, lyophilizate for the preparation of dosage forms and vaccines (Azoximer bromide), supplied by NPO Petrovax Pharm, LLC, Russia, 500 µg.

 
Excipients:
 

• Phosphate saline buffer solution up to 0.5 ml.

Description:	Colorless or yellowish, slightly opalescent liquid.
Presentation:	0.5 ml (1 dose) in ampules or vials, hermetically sealed with rubber stoppers and crimped with aluminum caps. 5 ampoules or vials are placed into a blister packaging of polyvinyl chloride film. 1 or 2 blisters together with Instruction on use per carton pack. Or 5 or 10 ampoules or vials without blister packaging are placed into a carton pack with a package insert.
Storage conditions:	Store away from light at the temperature of 2 to 8 °C. Keep out of reach of children. Do not freeze! Do not use the product which has been frozen. Shipping by all the types of roofed transport in lightproof containers temperature of 2–8 °C in conditions excluding freezing. Transportation is acceptable at a temperature of ≤ 25 °C for 6 hours.
Shelf life:	1 year. Do not use the product after the expiry date.
Manufacturer:	NPO Petrovax Pharm, LLC, Russia

Strictly confidential. Proprietary Information.  
[name]

Grippol® Plus is a trivalent inactivated polymer-subunit influenza vaccine:	
INN or generic name:	Influenza vaccine [inactivated] + Azoximer bromide
Dosage form:	suspension for intramuscular and subcutaneous injection.
Composition:	
One immunizing dose (0.5 ml) contains:
 
Active ingredients:
 

• Influenza type A virus (H1N1) antigen with hemagglutinin - 5 µg.

• Influenza type A virus (H3N2) antigen with hemagglutinin - 5 µg.

• Influenza virus subtype B antigen with hemagglutinin, 5 µg.

• Polyoxidonium®, lyophilizate for the preparation of dosage forms and vaccines (Azoximer bromide), supplied by NPO Petrovax Pharm, LLC, Russia, 500 µg.

 
Excipients:
 

• Phosphate saline buffer solution up to 0.5 ml.

Description:	Colorless or yellowish, slightly opalescent liquid.
Presentation:	0.5 ml (1 dose) in ampules or vials, hermetically sealed with rubber stoppers and crimped with aluminum caps. 5 ampoules or vials are placed into a blister packaging of polyvinyl chloride film. 1 or 2 blisters together with Instruction on use per carton pack. Or 5 or 10 ampoules or vials without blister packaging are placed into a carton pack with a package insert.
Storage conditions:	Store away from light at the temperature of 2 to 8 °C. Keep out of reach of children. Do not freeze! Do not use the product which has been frozen. Shipping by all the types of roofed transport in lightproof containers temperature of 2–8 °C in conditions excluding freezing. Transportation is acceptable at a temperature of ≤ 25 °C for 6 hours.
Shelf life:	1 year. Do not use the product after the expiry date.
Manufacturer:	NPO Petrovax Pharm, LLC, Russia

### Packaging and labeling

Upon arrival to the trial site, the primary and secondary packaging of the study drugs will be labeled in accordance with the requirements set forth in Federal Law No. 61 of the Russian Federation “On the Circulation of Medicines” and be marked “For clinical studies”.

---

Strictly confidential. Proprietary Information.  
[name]

Study vaccines in 0.5 ml ampoules will be supplied by NPO Petrovaks Farm, LLC in a package in accordance with the specification. Packages with the study drug were labeled as follows:

**Protocol:** GriQv-III-16

**Study Drug:** inactivated influenza vaccine

Suspension for intramuscular and subcutaneous injection.

1 ampule = 0.5 ml

Shake before use

**Code of the study drug:** 100, 200, or 300

**Trial site:**

**Investigator:**

**Batch:**

**Date of issue:**

**Expiry date:**

Store away from light at the temperature of 2 to 8 °C.

**Labeling:** "For clinical studies only"

### **Storage of study products**

Vaccines supplied for clinical studies should be kept in a restricted access area (i.e. in a locked cabinet) and in strict compliance with the conditions recommended by the manufacturer. The storage temperature should be checked and recorded daily. Dispensing and return of the unused product is reflected in the reports which were then transferred to NPO Petrovax Pharm, LLC. Vaccines and placebo should be stored in a place protected from light and inaccessible to children at a temperature of 2 to 8 °C (in the refrigerator).

Do not use the product that has been frozen.

Transportation is acceptable at a temperature of  $\leq 25$  °C for 6 hours.

### **Responsibility for storage of the drug**

All vaccine samples for the clinical study are transferred to the trial sites and stored strictly in accordance with the documentation. Unused vaccine samples must be returned to NPO Petrovax Pharm, LLC. Principal investigator is in charge of the proper product storage at the trial site.

The investigator should make accurate records of deliveries and release of the drug in a drug log. The accurate record containing the date and amount of drug administered to each volunteer should be available for inspection at any time.

---

Strictly confidential. Proprietary Information.  
[name]

All delivered drugs should be used only in accordance with this protocol, use for any other purpose is prohibited.

### **3.5. The duration of participation of subjects in the study, a description of the sequence and duration of all study periods**

The duration of participation of subjects in the study is  $183 \pm 5$  days. The study includes Screening (days (-3)– 0), Vaccination and Post-Vaccination Observation and Efficacy / Safety Evaluation (Days 1–180  $\pm$  5).

### **3.6. “Rules of discontinuation” and “Exclusion criteria” for individual subjects, parts of a study or study in general**

Since the present study does not provide for interim analysis of efficacy or safety, the “rules of discontinuation” of the entire study are not defined for these parameters.

If a volunteer withdraws participation from the study early, the investigator must document the reason for this withdrawal. Regardless of the reasons for why the volunteers drop out of the study early, they are not replaced since the sample size is calculated taking into account the early withdrawal of volunteers at a 5 % level.

In order for the Sponsor to evaluate the benefit and risk ratio for study subjects, an investigator is obligated to immediately notify the project manager of the CRO or the Sponsor about all the health risks that have arisen for each specific study subject who dropped out of the study. The study subject should also be notified about any new information on the study drug.

#### **Early termination of the entire study:**

Early termination criteria of the study include, but are not limited to:

- Sponsor's decision for medical or administrative reasons. The current review of medical data and information about the safety of study treatment together with the investigator is a standard procedure. As a result of this review, it may be decided to discontinue the study before all volunteers have completed it.
- Inability to recruit the needed number of volunteers.

In the event of early termination of the study, regardless of the reason for such decision, the sponsoring company will notify the investigator and the regulatory authorities in writing about study termination or suspension, indicating the reasons for its termination or suspension. LEC should be immediately notified about termination or suspension of the study with indication of the reasons for such decision. The investigator must immediately notify all volunteers and provide them with appropriate follow-up and, if necessary, further treatment.

---

Strictly confidential. Proprietary Information.  
[name]

### **Early termination of the study in a trial site:**

Criteria for early termination of the study in a trial site include, but are not limited to:

- The investigator is not complying with protocol requirements, the Helsinki Declaration, standards of the good clinical practice (ICH GCP) and the relevant requirements of regulatory authorities.
- The researcher provides false or incomplete information about the study to the Sponsor, CRO, LEC or regulatory authorities (including repeated omission of data entry in the CRF).
- The investigator cannot recruit the required number of volunteers within a specific period of time.
- The investigator withdraws his/her consent for study participation.

If the study is terminated prematurely or suspended for any reason, the investigator or the trial site should immediately notify the study subjects, verify the adequacy of their treatment and follow-ups and, if required by law, inform the regulatory authorities.

### **Early termination for separate volunteers:**

Volunteer's informed consent for study participation states that the volunteer has a right to terminate his/her participation in the study at any time and for any reason, and that the volunteer may terminate his/her participation in the study at the discretion of the investigator or the Sponsor, which should not affect the quality of medical care provided to him/her in the future.

The investigating physician should exclude a volunteer from the study (criteria for early termination of study participation) in a case of:

- Informed consent recall.
- Occurrence of a severe AE or serious adverse events.
- The volunteer is found to meet any of the non-inclusion criteria related to the safety of the volunteer participation in the study.
- If a female-volunteer becomes pregnant.
- The volunteer takes medicines not allowed in this study.
- The volunteer is lost to follow-up.
- In a situation, which, to the investigator's judgment, may adversely impact the volunteer if he/she continues participating in the study.
- For administrative reasons (study termination by the Sponsor or regulatory authorities) or in case of major protocol violations which may significantly impact the study results.

---

Strictly confidential. Proprietary Information.  
[name]

If any of these events occur, the investigator, whenever possible, immediately conducts an early study termination visit for the volunteer to evaluate safety and efficacy parameters.

The date of termination of study participation of a volunteer and the reason for early termination must be recorded in source documents and the CRF.

If a female volunteer drops out due to pregnancy, the investigator provides the sponsor with the information about the outcome of pregnancy (see Section 7.3.5).

Volunteers with unresolved adverse events are observed until the adverse event is resolved or until the condition is stabilized.

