#### **Evaluation of severity and duration of reported cases of influenza and ARI, complications:**

When recording a case of influenza or ARI, a study doctor will perform an evaluation of its duration, making additional telephone calls, where necessary, and determine its severity. In this study, a case with at least one of the complications listed below will be considered severe:

- the necessity of hospitalization,
- influenza-associated pneumonia,
- influenza-associated cardiovascular disorder,
- death.

---

Strictly confidential. Proprietary Information.  
[name]

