### 7.2. Methods and terms of evaluation, recording, and analysis of safety parameters

Evaluation of local and systemic reactions, as well as AEs, will be performed from the moment of immunization and within 6 months of follow-up. Recording of safety parameters will include the following procedures:

- clinical interview of a study subject;
- recording of thermometry results and complaints of a study subject related to his/her medical condition in a volunteer's diary;
- physical examination (including neurological status);
- vital signs;
- laboratory investigations
  - complete blood count and blood chemistry;
  - urinalysis;
  - evaluation of immunological parameters: serum immunoglobulin content (ELISA: IgE);
- quantitative assessment and nature (severity and duration) of local and systemic reactions to vaccine administration (reactogenicity);
- recording of AEs and SAEs associated with the study vaccines;
- recording of immediate type AEs, emerging within one hour after immunization;
- evaluation of incidence and nature of intercurrent disorders.

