### 7.3.2. Serious adverse events

A SAE is any AE corresponding to one or several criteria listed below:

- AE causing death of a volunteer.
- AE posing a threat to life of a volunteer.
- AE requiring hospitalization of a study subject or leading to extension of existing hospitalization, except for:
  - Optional treatment.
  - Monitoring of the study disease.

---

Strictly confidential. Proprietary Information.  
[name]

- For procedures as per the protocol, not associated with a deterioration in a volunteer's condition.
- Treatment of the existing disease, associated or not associated with the study disease, which has not worsened after administration of the first dose of the study product.
- Treatment received in an emergency unit due to an event which does not comply with the above mentioned criteria and which did not lead to hospitalization.
- AE leading to permanent or pronounced incapacity for work or disability.
- AE leading to congenital abnormalities / developmental diseases in children whose parents were exposed to the study product.

Apart from that, SAEs may include important medical manifestations in case when, based on the investigator's medical experience, such manifestations, if left untreated, may lead to one of the outcomes described above.

Death of a study subject is considered as an outcome of the AE. In case of death of a study subject, the investigator has to report medical condition of the study subject or the event causing the death, e.g., a disease, an accident, etc. as an SAE.

AE is considered as "posing a threat to life of a study subject" if it constitutes immediate danger to life of a study subject at the time of its development. This category does not include AEs, which could theoretically lead to subject's death if their severity was higher.

According to SAE criteria, hospitalization is considered as inpatient treatment for more than one calendar day, i.e. a hospital stay for at least one night.

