#### *Efficacy analysis*

The following immunogenicity parameters will be presented with the respective two-sided 95 % confidence intervals for antigens and therapeutic groups:

Before and after immunization:

- Geometric mean antibody titers (GMAT).
- The share of subjects achieving seroconversion.

After immunization:

- The share of subjects achieving seroconversion.
- Coefficient of increase of mean geometric antibody titer versus baseline before immunization (GMAT ratio before and after immunization).

Efficacy parameters will be evaluated by available data, without restoration of missing data.

Testing of statistical hypotheses will be performed for Group A (Grippol® Quadri vaccine) as compared with:

- pooled data of groups B and C (Grippol® Plus) for antigens H1N1 and H3N2, separately for each antigen;
- data of group B for Yamagata lineage antigen;
- data of group C for Victoria lineage antigen.

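### Section 3.6 ends a volunteer's data collection after a severe AE, an SAE or a prohibited medicine, although the only dose has already been given

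*Combined protocol and SAP*

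**What the plan says.** Section 3.6, under early termination for separate volunteers, introduces its list with "The investigating physician should exclude a volunteer from the study (criteria for early termination of study participation) in a case of". The list includes "Occurrence of a severe AE or serious adverse events", with no condition that the event be related to vaccine, and "The volunteer takes medicines not allowed in this study". The synopsis repeats it in mandatory wording. Section 3.4 provides for one intramuscular dose. Table 2 has the exclusion criteria checked at every contact up to Visit 11 (Day 180±5).

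For an excluded volunteer, Section 3.6 provides two things: an immediate early termination visit, where possible, covering safety and efficacy parameters, and observation of unresolved AEs until they resolve or stabilise. Sections 7.3.3 and 7.4 likewise follow SAEs and AEs to resolution or stabilisation. No section keeps the Visit 7 blood draw or the calls for that volunteer, or says how a titer taken at an early visit is analysed.

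Section 7.2 says that evaluation of reactions and AEs "will be performed from the moment of immunization and within 6 months of follow-up", and Section 6.2 records influenza and ARI over the same period. Section 8.1 states: "Efficacy parameters will be evaluated by available data, without restoration of missing data". Section 3.6 rules out replacement and relies on the 5 % allowance in the sample size. Section 8.5 keeps every vaccinated volunteer in the safety set and everyone with at least one titer in the FAS. The per-protocol set requires titers before and after vaccination on schedule, no prohibited drug, and completion of the study.

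**The concern.** In a multi-dose trial, a rule of this kind protects the volunteer by stopping further doses. Here nothing is left to stop once Day 0 has passed. What ends is observation, and it ends because of something that happened after vaccination and that may depend on the vaccine or on the illness under study. With an available-data analysis, three results are exposed:

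- the seroconversion comparison, for events before Visit 7;
- the 6-month AE record, for events at any time;
- influenza/ARI incidence, where a volunteer excluded before a first episode is censored for a reason that may not be independent of the outcome.

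The third applies to prohibited drugs too. Section 5.2.1 bars acetylsalicylic acid, as an antiaggregant, for the whole study. A volunteer who takes it for a headache or for early ARI symptoms therefore falls under the rule.

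**Working it through.** **1. What is lost, by timing of the event** (Sections 3.6, 6.2, 7.3.3, 7.4, 8.5)

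| | Event before Visit 7 | Event after Visit 7 |
|---|---|---|
| Day 22±1 titer | Not planned; early visit where possible | Already taken |
| Calls, Visits 8–11 | All four stop | The remaining ones stop |
| The triggering AE/SAE | Followed to resolution or stabilisation | Same |
| Later AEs and ARI episodes | No planned capture, though a related SAE stays reportable | Same |
| FAS | Member through the baseline titer, but without a seroconversion outcome unless an early-visit titer is accepted | Member with outcome |
| Per-protocol | Out: no on-schedule second titer | Doubtful: the set requires study completion |

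**2. Hospitalised influenza/ARI.** Section 6.2 says "a case with at least one of the complications listed below will be considered severe", and the list includes need for hospitalisation. Section 7.3.2 counts as an SAE an "AE requiring hospitalization of a study subject or leading to extension of existing hospitalization" and defines hospitalisation as a stay of at least one night. A hospitalised case with an overnight stay is therefore an SAE and triggers exclusion under Section 3.6.

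**3. The plan's own sample size** (Section 8.2: reference 60 %, difference 1 %, margin 15 %, one-sided 2.5 %, power 80 %)

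n = (1.960 + 0.842)² / (0.15 − 0.01)² × [0.60 × 0.40 + 0.59 × 0.41] = 192.98, so 193 per group.

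193 / 0.95 = 203.2, so 204 per group and 612 in total. Both figures reproduce. The allowance for all causes of loss is 204 − 193 = 11 per group.

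**4. Power under assumed total loss**, for a 1:1 comparison (A with B, or A with C), by the same normal approximation. The documents give no expected rate for these triggers.

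| Loss | Evaluable per arm | Power |
|---|---|---|
| 0 % | 204 | 82.1 % |
| 5 % | 193 | 80.0 % |
| 10 % | 183 | 77.9 % |
| 20 % | 163 | 73.1 % |

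A against pooled B and C stays at 84 % or more throughout.

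**5. How many volunteers could be affected.** Phase I (Section 1.3) reports no severe AE and no SAE. With zero events in N, the one-sided 95 % upper bound is 1 − 0.05^(1/N):

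- N = 30 (Quadri): 9.5 %, about 19 of 204
- N = 60 (both vaccines): 4.9 %, about 10 of 204
- N = 90 (all, including placebo): 3.3 %, about 7 of 204

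The number could be close to zero or could use up the whole allowance.

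**6. Possible bias in R − T** (true value +1.0 point; fractions removed before Visit 7 are assumed)

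- Extreme, 5 % of each arm, removed test volunteers all non-responders and removed reference volunteers all responders: T = 0.59/0.95 = 0.621; R = (0.60 − 0.05)/0.95 = 0.579; R − T = −4.2 points. This is a shift of 5.2 points towards non-inferiority, about a third of the margin.
- Opposite extreme: T = (0.59 − 0.05)/0.95 = 0.568; R = 0.60/0.95 = 0.632; R − T = +6.3 points, a shift of 5.3 points the other way.
- Moderate, removed volunteers seroconvert 20 points less often than those retained, 5 % removed in each arm: T = 0.59 + 0.05 × 0.20 = 0.600; R = 0.60 + 0.05 × 0.20 = 0.610; no shift.
- Same, but 5 % of test and 1 % of reference removed: T = 0.600; R = 0.602; R − T = +0.2, a shift of 0.8 points.

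**The case against.** The strongest reply is that the plan already covers most of this. The triggering event is followed to resolution, and related SAEs remain reportable after the study. Extra calls under Section 6.2 can establish the duration of an ARI case, and the first ARI episode is already counted in the Kaplan-Meier analysis. The safety set and FAS keep the volunteer as a member, and prohibited drugs are already in the per-protocol definition. No section forbids a Day 22 draw after exclusion. All of that stands, and it narrows the point to what follows the triggering event and to the titer when the event precedes Visit 7.

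It also defeats several stronger readings that a reader might infer:

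- *Every excluded volunteer loses the Day 22 titer.* Only those with an event before Visit 7 do.
- *Any listed drug on any day triggers exclusion.* Section 5.2.1 bars antipyretics, temperature-affecting products and physiotherapy only at screening and on the immunisation day. CNS depressants, cytotoxics, anticoagulants and antiaggregants are barred throughout.
- *Phase I shows that removal will differ by arm.* Systemic reactions were 20.7 % with Quadri and 3.6 % with Plus, but all were mild and no significant difference was reported. None would have met the trigger.
- *A hospitalised ARI case goes unrecorded.* The current episode is followed; later episodes are not.
- *Section 3.6 flatly contradicts Sections 6.2 and 7.2.* A general schedule and individual withdrawal criteria can coexist. The gap is that the plan provides no data collection after exclusion.

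What the objection does not answer is that an immediate visit, made only where possible, is not a Day 22 sample, and that following one ongoing event is not follow-up to Day 180.

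**Conclusion.** The concern holds in this limited form and should be corrected. As written, the plan ends scheduled observation at a post-vaccination event without stopping any exposure, and then analyses whatever data remain. The result is selective missingness in the titer for early events, and in later AEs, ARI episodes and per-protocol membership for all of them.

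The size cannot be estimated from the documents. The 5-point bounds require an assumed 5 % removal in each arm before Visit 7 and opposite extremes of response in the two arms. The moderate scenarios give 0 to 0.8 points against a 15-point margin, and the direction is not known in advance. The power cost is minor, about 2 points at 10 % total loss. A reader might infer that the sample size or the non-inferiority conclusion is in jeopardy; the figures do not support that. The safety and influenza/ARI follow-up is the more exposed part, because the rule operates over all 180 days and not only the first 22.

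Separately, Section 5.3 makes withdrawal for concomitant-therapy non-compliance optional, while Section 3.6 words exclusion for a prohibited medicine as required. These need to be reconciled.

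**What to change.** Leave the listed criteria and all clinical decisions with the investigator, and separate them from data collection. State that, unless consent is withdrawn or the volunteer is lost to follow-up, the already scheduled Visit 7 serology and safety assessments and the calls to Day 180 continue. State that these data are analysed in the safety set and the FAS, and that prohibited-drug use is handled through the existing per-protocol definition. Say how a titer taken at an early termination visit enters the FAS and the per-protocol set, and what study completion means for the latter.

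Reconcile the required wording of Section 3.6 (and the synopsis) with the optional wording of Section 5.3, and Section 3.6 with the 6-month follow-up in Sections 6.2 and 7.2.

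The cost is amendment wording, with the approvals that Sections 11.2 and 11.3 require, plus a few contacts that are already in the schedule. No new visit type or extra sample is needed.
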